7. PLANNED ANALYSIS

The combined SRD parts and FE part will be evaluated separately.

In the combined SRD parts, the placebo group under fasting (labelled “Placebo fast”) and the placebo group under fed conditions (labelled “Placebo fed”) will be compared, as well as the combined placebo group (labelled “Placebo total”) to all active treatment groups.

Safety analysis (refer to [Section 7.8](#)) will be performed by _____ and will be presented in Sections 15.1 to 15.4 of the CTR and in Appendix 16.2 and 16.1.13.1.

Inferential statistical analyses of PK endpoints (refer to Sections [7.4](#) and [7.5.2](#)) will also be performed by _____ and will be presented in Section 15.5 of the CTR and in Appendix 16.1.13.3.

Descriptive data analysis of PK parameters and concentrations will be performed by BI and will be presented in Section 15.6 of the CTR.

Descriptive data analysis of PD endpoints will be performed by department Translational Medicine and Clin. Pharmacology at BI and will be presented in Section 15.7 of the CTR.

The format of the listings and tables will follow the standards defined in the BI corporate guideline “Reporting of Clinical Trials and Project Summaries” [001-MCG-159] [\(6\)](#) with the exception of those generated for PK-calculations.

In the combined SRD parts, the individual values of all subjects will be listed, sorted by treatment group, subject number, and visit.

In the FE part, the individual values of all subjects will be listed, sorted by treatment sequence, subject number, visit and actual treatment (if appropriate).

The listings will be included in Appendix 16.2 of the CTR.

For end-of-text tables, the set of summary statistics for non-PK parameters is:

N	number non-missing observations
Mean	arithmetic mean
SD	standard deviation
Min	minimum
Median	median
Max	maximum

For analyte concentrations as well as for all PK parameters, the following descriptive statistics will additionally be calculated:

CV	arithmetic coefficient of variation
gMean	geometric mean
gCV	geometric coefficient of variation

The data format for descriptive statistics of concentrations will be identical with the data format of the respective concentrations. The descriptive statistics of PK parameters will be calculated using the individual values with the number of decimal places as provided by the evaluation program. Then the individual values as well as the descriptive statistics will be reported with three significant digits in the CTR.

Tabulations of frequencies for categorical data will include all possible categories and will display the number of observations in a category, as well as the percentage (%) for each treatment group/sequence. Percentages will be rounded to one decimal place and will be based on all subjects in the respective subject set whether they have non-missing values or not. The category 'missing' will be displayed only if there are actually missing values.

Units of variables should be given in the titles or column/row descriptors in square brackets (e.g. [mg]).

Exclusion of PK parameters

The analysis data set (ADS) ADPP (PK parameters) contains column variables APEXC and APEXCO indicating inclusion/exclusion (APEXC) of a PK parameter and an analysis flag comment (APEXCO). All analyses based on the PKs will include parameters if they are not flagged for exclusion, that is APEXC is equal to “Included”.

Exclusion of PK concentrations

The ADS ADPC (PK concentrations per time-point or per time-interval) contains column variables ACEXC or ACEXCO indicating inclusion/exclusion (ACEXC) of a concentration and an analysis flag comment (ACEXCO). Exclusion of a concentration depends on the analysis flag comment ACEXCO. For example, if ACEXCO is set to ‘ALL CALC’, the value will be excluded for all types of analyses based on concentrations. If ACEXCO is set to ‘DESC STATS’, the value will be excluded from descriptive evaluations per planned time point/time interval. If ACEXCO contains the addition ‘TIME VIOLATION’ or ‘TIME DEVIATION’, the value can be used for further analyses based on actual times. If ACEXCO is set to ‘HALF LIFE’, the value will be excluded from half-life calculation (and, as a consequence, any calculation that relies on λ_z) only; the value is included for all other analyses.

Further details are given in 001-MCS-36-472_RD-01 “Noncompartmental Pharmacokinetic / Pharmacodynamic Analyses of Clinical Studies” (5) and 001-MCS-36-472_RD-03 “Description of Analytical Transfer Files and PK/PD Data Files” (7).

7.1 DEMOGRAPHIC AND OTHER BASELINE CHARACTERISTICS

Only descriptive statistics are planned for this section of the report, based on the TS.

The data will be summarised by treatment group and in total (combined SRD parts). The data of the FE part will be summarised by treatment sequence and in total.

For public disclosure, both trial parts will be combined. In case that a subject participate in both trial parts, the information from the prior participation will be used for total baseline characteristics.

7.2 CONCOMITANT DISEASES AND MEDICATION

Frequency tables are planned for this section of the report, based on the TS.

Concomitant diseases will be coded using the coding system of the Medical Dictionary for Drug Regulatory Activities (MedDRA). Medications will be coded using the World Health Organization Drug Dictionary (WHO-DD). The coding version number will be displayed as a footnote in the respective output.

The diagnoses and medications will be listed. Subjects without any concomitant diagnoses or concomitant therapies should be marked with a “No” in the respective column.

The relevance of the concomitant therapies to the evaluation of PK will be decided no later than at the RPM/DBLM.

7.3 TREATMENT COMPLIANCE

Section 4.3 of the CTP: *Compliance will be assured by administration of all trial medication in the study centre under supervision of the investigating physician or a designee. The measured plasma concentrations and/or urinary excretion will provide additional confirmation of compliance.*

It is not intended to list the compliance separately. Any deviations from complete intake will be addressed in the RPM/DBLM (cf. TSAP [Section 6.2](#)) and described in the CTR.

7.4 PRIMARY ENDPOINTS

Safety evaluation – combined SRD parts under fasting and fed conditions

Refer to TSAP [Section 7.8](#) for a description of the analysis of safety and tolerability of BI 705564.

Investigation of relative bioavailability (food effect evaluation) – FE part

Relative bioavailability is to be determined on the basis of the primary and secondary PK parameters (AUC_{0-tz} , C_{max} and $AUC_{0-\infty}$). Those parameters will be ln-transformed (natural logarithm) prior to fitting the model.

Primary analysis

Section 7.1.3 of the CTP: *The statistical model used for the analysis of primary (AUC_{0-tz} and C_{max}) and [...] secondary ($AUC_{0-\infty}$) endpoints will be an ANOVA (analysis of variance) model on the logarithmic scale. This model will include effects accounting for the following sources of variation: ‘sequence’, ‘subjects within sequences’, ‘period’ and ‘treatment’. The*

effect 'subjects within sequences' will be considered as random, whereas the other effects will be considered as fixed. The model is described by the following equation:

$$y_{ijkm} = \mu + \zeta_i + s_{im} + \pi_j + \tau_k + e_{ijkm}, \text{ where}$$

y_{ijkm} = logarithm of response (AUC_{0-tz} , C_{max} , $AUC_{0-\infty}$) measured on subject m in sequence i receiving treatment k in period j ,

μ the overall mean,

ζ_i the i th sequence effect, $i = 1, 2$

s_{im} the effect associated with the m^{th} subject in the i^{th} sequence, $m = 1, 2, \dots, n_i$

π_j the j th period effect, $j = 1, 2$

τ_k the k th treatment effect, $k = 1, 2$

e_{ijkm} the random error associated with the m^{th} subject in sequence i who received treatment k in period j .

The difference between the expected means for test treatments (tablets under fed conditions, T) and reference treatment (tablets under fasting conditions, R) $\ln(T)-\ln(R)$, will be estimated by the difference in the corresponding Least Square Means (point estimate) and two-sided 90% confidence intervals based on the t-distribution will be computed. These quantities will then be back-transformed to the original scale to give the point estimator (geometric mean) and interval estimates for the ratio between response under test and response under reference.

The analysis will be accomplished by using the XPKISTAT macro, based on PKS (design BWC).

7.5 SECONDARY ENDPOINTS

7.5.1 Key secondary endpoints

This section is not applicable as no key secondary endpoints have been specified in the protocol.

7.5.2 Secondary endpoints

Assessment of dose proportionality - SRD parts under fasting and fed conditions

Section 7.3.2 of the CTP: *Two separate analyses will be performed, one for the doses under fasting conditions, and one for the doses under fed conditions.*

Dose proportionality of the PK endpoints $AUC_{0-\infty}$ and C_{max} in plasma of BI 705564 will be explored using the power model that describes the functional relationship between dose and PK endpoints. The basic model consists of a regression model applied to ln-transformed data. The corresponding ANCOVA (Analysis of Covariance) model includes the logarithm of the dose as a covariate.

The model is described by the following equation:

$$Y_{ij} = \alpha + \beta * X_i + \varepsilon_{ij}$$

where

Y_{ij}	logarithm of the pharmacokinetic endpoint for subject j at dose level i; $j = 1, 2, \dots, N,$
α	intercept parameter;
β	slope parameter;
X_i	logarithm of dose i;
ε_{ij}	random error associated with subject j at dose level i (assumed to be independent and identically normally distributed).

Section 7.3.2 of the CTP: *This equation can be fit as a linear regression model.*

Based on the estimate for slope parameter (β), a 2-sided 95% CI for the slope will be computed. Perfect dose proportionality would correspond to a slope of 1. The assumption of a linear relationship between the ln-transformed pharmacokinetic endpoint and the ln-transformed dose will be checked.

If dose proportionality over the entire dose range investigated cannot be shown, an attempt will be made to identify dose range(s), where dose proportionality can be assumed.

This analysis will be accomplished by using the XPKISTAT macro (design DB), based on the PKS.

To support the analyses of dose proportionality, a regression plot will be performed, where the logarithm of dose is depicted versus logarithm of PK endpoint, including the estimated regression line from the power model and reference line of perfect proportionality ($\beta=1$).

A joint analysis (fasting and fed conditions) of dose proportionality will not be performed.

Investigation of relative bioavailability (food effect evaluation) – FE part

Refer to TSAP [Section 7.4](#) for a description of the analysis of food effect for the secondary endpoint $AUC_{0-\infty}$.

Safety

Refer to TSAP [Section 7.8](#) for a description of the analysis of safety and tolerability of BI 705564.

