No. of subjects planned:  total entered: each treatment:	
92*
 
(1) Single rising dose part under fasting conditions: 48 8 per dose group (6 on active drug and 2 on placebo)
 
(2) Food effect part: 12 (all on active drug)
 
(3) Single rising dose part under fed conditions: 32* 8 per dose group (6 on active drug and 2 on placebo)
 
* Additional subjects may be entered to allow testing of additional doses on the basis of experience gained during the trial conduct (e.g. preliminary PK data), provided the planned and approved highest dose will not be exceeded. Thus, the actual total number of subjects entered in the study may exceed 92 (32 in single rising dose part under fed conditions), but will not exceed 108 (48 in single rising dose part under fed conditions) subjects entered.
		
Diagnosis:	Not applicable		
Main criteria for inclusion:	Healthy male subjects, age of 18 to 50 years (inclusive), body mass index (BMI) of 18.5 to 29.9 kg/m  (inclusive)		
(1) Single rising dose part under fasting conditions			
Test products:  dose:  mode of admin.:	
BI 705564 as solution (powder for oral solution [PfOS], 0.25 mg/mL) and film-coated tablet (10 mg)
 
Solution (PfOS): 1 mg, 3 mg q.d. Tablet: 10 mg, 20 mg, 40 mg, 80 mg q.d.
 
Oral with 240 mL of water after an overnight fast of at least 10 h
		
Comparator products:  dose:  mode of admin.:	
Matching placebo as solution (i.e. solvent) and film-coated tablet formulation
 
Not applicable
 
Oral with 240 mL of water after an overnight fast of at least 10 h
		
(2) Food effect part			
Test product:  dose:  mode of admin.:	
Fed: BI 705564 as film-coated tablet formulation (10 mg tablets)
 
Tablet: 10 mg q.d.
 
Oral with 240 mL of water after a high-fat, high-calorie meal
		

Name of company: Boehringer Ingelheim		Tabulated Trial Protocol	
Name of finished product: Not applicable			
Name of active ingredient: BI 705564			
Protocol date: 15 FEB 2017	Trial number: 1408-0001		Revision date: 11 SEP 2017
Comparator products:	Matching placebo as film-coated tablet formulation		
dose:	Not applicable		
mode of admin.:	Oral with 240 mL of water after a high-fat, high-calorie breakfast		

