## 2.2 TRIAL OBJECTIVES

The primary objective of the single rising dose parts under fasting and under fed conditions is to investigate safety and tolerability of BI 705564 in healthy male subjects following oral administration of single rising doses. Secondary objectives are the exploration of

pharmacokinetics (PK) including dose proportionality, and pharmacodynamics (PD) of BI 705564 after single rising doses.

The objective of the food effect part is to explore the relative bioavailability of BI 705564 tablets under fed and fasting conditions following the oral administration of single doses.

A description of the endpoints to be determined, and the observations along with specific information as how to collect the data, is provided in [Section 5](#).

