### 3. DESCRIPTION OF DESIGN AND TRIAL POPULATION

#### Global Amendment No 4 – major changes in Section 3:

Originally, the study was planned to consist of two study parts: (1) SRD part under fasting conditions consisting of 8 dose groups (1 to 160 mg) à 8 volunteers (64 volunteers in total) and (2) food effect part investigating the effect of a high-fat, high-calorie breakfast on doses of 10 mg and 40 mg in 12 volunteers each, i.e. in 24 volunteers total.

Data obtained during the trial indicate that no relevant increase of exposure was to be expected with dose groups 120 mg and 160 mg in the SRD part under fasting conditions. Therefore, the two highest dose groups of the SRD part under fasting conditions (120 mg and 160 mg) are not dosed. Data of the food effect part 10 mg indicate that relative bioavailability of BI 705564 tablet may be increased by food. The food effect part 40 mg is not dosed. Instead, a third study part is added. A SRD part under fed conditions is added to the study and is designed to investigate single rising oral doses of BI 705564 after a high-fat, high-calorie breakfast. It is planned to apply BI 705564 to 4 dose groups à 8 volunteers per group (32 volunteers in total) with the possibility to add up to 2 interim dose groups in the SRD part under fed conditions (see Section 3.1, “Single rising dose part under fed conditions”).

See [Appendix 11](#) for details.

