### **Single rising dose part under fed conditions**

This part is designed single-blind, partially randomised, and placebo-controlled within parallel dose groups.

A total of 32 healthy male subjects is planned to participate in the single rising dose part under fed conditions, resulting in 4 sequential groups comprising 8 subjects each. However, additional subjects may be entered to allow testing of additional doses on the basis of the experience gained during the conduct of the trial (e.g. preliminary PK data), provided that the planned and approved highest dose will not be exceeded. Thus, the actual number of subjects entered in the single rising dose part may exceed 32, but will not exceed 48 subjects entered. Such changes may be implemented via non-substantial CTP amendments.

Within each dose group, 6 subjects will receive the active drug and 2 will receive placebo. Only one dose is tested within each dose group. Dose groups will be treated consecutively in ascending order of doses. Each dose group will consist of 2 cohorts of 4 subjects each (3 on active drug and 1 on placebo).

On the first study day within each dose group, the first cohort will be treated in a single-blind manner in the following order: First subject (active) followed at least 1 hour later by the second subject (placebo) followed at least 1 hour later by the third subject (active) followed at least 10 minutes later by the fourth subject (active).

If BI 705564 treatment is safe and showed acceptable tolerability in the first cohort, subjects in the second cohort will be treated not earlier than 2 days later (at least 46 h between the 1st subject of each cohort) in a single-blind, randomised manner. In the second cohort, a time interval of at least 10 minutes will be maintained between administrations of trial drug to the individual subjects.

A time interval of at least 10 days will be maintained between the first drug administration in the previous dose group and the first drug administration of the subsequent dose group. The dose groups to be evaluated are outlined in Table 3.1: 2 below.

Table 3.1: 2 Dose groups in the single rising dose part under fed conditions

Dose Group	7	8	12*	13*
Dose (mg) q.d.	20	40	80	160
Formulation	Tab	Tab	Tab	Tab
Number of subjects	8	8	8	8
Subjects with placebo	2	2	2	2
Subjects with active drug	6	6	6	6

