#### Assessment of dose proportionality

Dose proportionality will be assessed using the secondary pharmacokinetic endpoints as specified in [Section 5.5.1.2](#). Two separate analyses will be performed, one for the doses under fasting conditions, and one for the doses under fed conditions.

The basic model for the investigation of dose proportionality will be a power model that describes the functional relationship between the dose and PK endpoints.

$$\exp(Y_{ij}) = \alpha' * \exp(X_i)^\beta * \varepsilon'_{ij}$$

The model consists of a regression model applied to log-transformed data. The corresponding ANCOVA model includes the logarithm of the dose as a covariate.

Together with  $\alpha' = \exp(\alpha)$  and  $\varepsilon'_{ij} = \exp(\varepsilon_{ij})$ , taking natural logarithms converts this model to a linear form as follows:

$$Y_{ij} = \alpha + \beta * X_i + \varepsilon_{ij}$$

where

$Y_{ij}$	logarithm of the pharmacokinetic endpoint for subject j at dose level i; j = 1, 2, ..., N;
$\alpha$	intercept parameter;
$\beta$	slope parameter;
$X_i$	logarithm of dose i;
$\varepsilon_{ij}$	random error associated with subject j at dose level i (assumed to be independent and identically normally distributed).

This equation can be fit as a linear regression model.

Based on the estimate for slope parameter ( $\beta$ ), a 2-sided 95% CI for the slope will be computed. Perfect dose proportionality would correspond to a slope of 1. The assumption of a linear relationship between the log-transformed pharmacokinetic endpoint and the log-transformed dose will be checked.

If dose proportionality over the entire dose range investigated cannot be shown, an attempt will be made to identify dose range(s), where dose proportionality can be assumed.

Graphical displays: To support the analyses of dose proportionality, graphical representations of the data might be created. These might include (but are not limited to) individual time-courses of trough plasma concentrations and the gMean plasma concentration time profiles.

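### In the readable text, the fasting dose-proportionality slope spans a switch from oral solution (1–3 mg) to tablets (10–80 mg) with no formulation term, and no fasting tablet-only slope is pre-specified beside it

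*SAP*

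**What the plan says.** The fasting treatments are listed in the Protocol Synopsis as "Solution (PfOS): 1 mg, 3 mg q.d. Tablet: 10 mg, 20 mg, 40 mg, 80 mg q.d". Protocol Tables 3.1: 1 and 4.1.4: 1 and SAP Table 6.1: 1 agree. No dose is given in both forms, and each dose group has 6 subjects on active drug.

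Protocol 7.3.2 splits the analysis only by food: "Two separate analyses will be performed, one for the doses under fasting conditions, and one for the doses under fed conditions". SAP 7.5.2 gives the model as Y = α + β·ln(dose) + error for AUC0-∞ and Cmax, with a two-sided 95% CI for β and 1 as the value for perfect proportionality: "The corresponding ANCOVA (Analysis of Covariance) model includes the logarithm of the dose as a covariate". It adds a check of linearity (no method stated), a log-log regression plot with the slope-1 line, and a conditional fallback ("If dose proportionality over the entire dose range investigated cannot be shown, an attempt will be made to identify dose range(s"). It also says: "A joint analysis (fasting and fed conditions) of dose proportionality will not be performed".

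The fed part uses tablets only, 20 to 160 mg (Protocol Table 3.1: 2, "Dose groups in the single rising dose part under fed conditions"). Protocol 2.2 names the secondary objective as exploring "pharmacokinetics (PK) including dose proportionality, and pharmacodynamics (PD) of BI 705564 after single rising doses".

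**The concern.** Formulation changes once along the fasting dose axis, between 3 and 10 mg, and ln(dose) is the only regressor. Any solution/tablet difference in bioavailability therefore enters the slope and is reported as dose dependence. The slope could move away from 1 because of the switch alone, or stay near 1 because the switch offsets flattening within the tablets.

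Some flattening is plausible. The amendment note at the start of Protocol Section 3 says that data from the trial indicated "no relevant increase of exposure was to be expected with dose groups 120 mg and 160 mg in the SRD part under fasting conditions". It gives no slope and no curve shape.

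The fed slope does not fill the gap. It is free of the formulation switch but describes fed dosing, and comparing it informally with the fasting slope would mix food with formulation. At stake is the reading of one exploratory secondary result.

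**Working it through.** The documents give no slope, precision or power for dose proportionality, so there is no plan figure to reproduce.

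**Inputs from the documents:** doses 1, 3 (solution) and 10, 20, 40, 80 mg (tablet); 6 active subjects per dose; two-sided 95% CI. **Assumptions, not in the documents:** F, the between-subject gCV, and the slopes within each form.

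**1. How much of F enters the slope.** Let x = ln(dose) = 0, 1.099, 2.303, 2.996, 3.689, 4.382 (mean 2.411), and z = 1 for tablets.
- Sxx = Σ(x − 2.411)² = 13.407 per replicate.
- Sxz = 4 × (3.342 − 2.411) = 3.724, where 3.342 is the tablet mean of x.
- Coefficient = 3.724 / 13.407 = 0.278. The correlation of x with z is 0.88.

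If both forms share slope β, the expected pooled slope is β + 0.278 × ln(F).

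**2. Proportional within each form (β = 1).** For example, at F = 0.7: 1 + 0.278 × (−0.357) = 0.90. The last three columns give the share of simulated trials whose 95% CI excludes 1.

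| F | Pooled slope | gCV 30% | gCV 40% | gCV 50% |
|---|---|---|---|---|
| 0.7 | 0.90 | 82% | 59% | 44% |
| 0.8 | 0.94 | 44% | 28% | 20% |
| 1 | 1.00 | 5% | 5% | 5% |
| 1.25 | 1.06 | 44% | 28% | 20% |
| 1.5 | 1.11 | 90% | 70% | 53% |

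**3. Can the switch hide tablet flattening?** Take F = 1.25, which alone adds 0.278 × 0.223 = 0.062, with a solution slope of 1.
- *Constant tablet slope 0.8, F defined at 10 mg.* Over the tablets, Σ(x − 2.411)(x − 2.303) = 6.274. The slope falls by 0.2 × 6.274 / 13.407 = 0.094, giving 1 + 0.062 − 0.094 = 0.968.
- *Same tablet slope, F defined at 3 mg.* A further 0.2 × ln(10/3) × 0.278 = 0.067 comes off, giving 0.90.
- *Hard plateau* (80 mg exposure equal to 40 mg, otherwise proportional). The slope falls by ln 2 × 1.971 / 13.407 = 0.102, giving 0.96.
- *Soft plateau* (80 mg exposure 1.2 times that at 40 mg). It falls by ln(2/1.2) × 1.971 / 13.407 = 0.075, giving 0.99.

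The next table uses gCV 40%. Neither signal means that the pooled CI includes 1 and a 5% lack-of-fit F-test (4 and 30 df) does not reject. That test is an assumption, because the SAP names no method.

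| Tablet curve, F = 1.25 | Neither signal | Tablet-only CI excludes 1 |
|---|---|---|
| Constant 0.8, F at 10 mg | 69% | 47% |
| Constant 0.8, F at 3 mg | 36% | 47% |
| Soft plateau at 80 mg | 43% | 49% |
| Hard plateau at 80 mg | 18% | 73% |

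**4. Precision of a tablet-only slope.** With six subjects per dose, Sxx is 6 × 13.407 = 80.44 pooled and 6 × 2.402 = 14.41 for tablets only. At gCV 40% the log SD is √ln(1.16) = 0.385.
- Pooled: SE = 0.385/√80.44 = 0.043; half-width 2.032 × 0.043 = 0.087 (34 df).
- Tablet-only: SE = 0.385/√14.41 = 0.1015; half-width 2.074 × 0.1015 = 0.210 (22 df).
- Ratio: 0.210/0.087 = 2.4.
- The tablet-only CI excludes 1 in 16% of trials if the true slope is 0.9 and in 47% if it is 0.8.
- If both forms share one slope, the pooled estimate has the smaller root mean squared error while |ln F| < √(0.1015² − 0.043²)/0.278 = 0.331, that is, for F from 0.72 to 1.39.

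**The case against.** The strongest reply is that the plan already contains most of what is needed. The analysis is exploratory, and Protocol 7.2 treats intervals as estimates, not tests. The linearity check and the plot could show a step between 3 and 10 mg, the sub-range search could arrive at 10 to 80 mg, and treatment labels identify formulation, so a reader could refit the tablets. The added slope is imprecise.

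Much of this stands, and it keeps the point minor. It does not remove it. The search is conditional, its ranges are chosen after seeing the data, and nothing readable mentions formulation. None of these steps guarantees a tablet-only estimate.

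Three stronger readings are tempting and not supported:
- *That masking would usually go unnoticed.* The 69% figure belongs to one curve with F fixed at 10 mg. A plateau at the top dose, closer to what the protocol describes, gives 18% to 43%. In both plateau cases the two planned signals, with the assumed test, catch more (82% and 57%) than the tablet-only CI (73% and 49%).
- *That the sub-range search starts whenever the CI excludes 1.* The SAP does not define its trigger that way, so the exclusion rates above describe the interval, not a planned decision.
- *That the sponsor had no solution/tablet information or no tablet-only analysis anywhere.* Protocol 2.1.2 to 2.1.5 are largely blanked, and Protocol 1.2 and 7.3.3 and parts of the SAP cannot be read. SAP 7.5.2, where such a slope belongs, is readable and has none.

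**Conclusion.** The point holds in limited form and is minor. On the readable text, one fasting slope covers two formulations and carries 0.278 × ln(F). The structure and the coefficient follow directly from the design. The size does not: it rests on assumed values of F, gCV and within-form slopes, and it is zero at F = 1. Over F from 0.7 to 1.5 with proportionality within each form, the slope runs from 0.90 to 1.11, against a pooled half-width of 0.087 at gCV 40%. Masking of tablet flattening is possible but depends on curve shape and on the dose at which F applies.

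A reader might infer that dose escalation or the safety conclusion is affected. The documents do not support that. Escalation rests on safety review and preliminary exposure data (Protocol 3.1 and 7.3.5), and the primary endpoint of the rising-dose parts is drug-related adverse events. Only the interpretation of an exploratory secondary objective is touched.

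**What to change.** In SAP 7.5.2, pre-specify a fasting tablet-only power-model slope (10, 20, 40 and 80 mg) with a two-sided 95% CI for AUC0-∞ and Cmax, as a supportive analysis that is always reported beside the pooled six-dose slope. Add a sentence saying that the pooled slope, and any proportional range spanning 3 to 10 mg, includes the change from solution to tablet. The two slopes should be read together, and the pooled slope should stay.

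The cost is SAP wording and one extra fit per endpoint on existing data. The tablet-only CI is about 2.4 times wider and its power is low, so it cannot replace the pooled estimate. A six-dose model with a formulation term would be slightly tighter (half-width 0.185 at gCV 40%), but it assumes that solution and tablets share one slope.
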